# **LABORATORY TESTING**

Patients requiring transfusions intraoperatively or post-operatively are currently already assessed via ROTEM pre and post product transfusions to guide product selection for clinical purposes. A ROTEM transfusion algorithm is already in use for both cardiovascular surgery and liver transplant. All laboratory testing will be standard of care for labs and ROTEM. Patients will have a ROTEM performed on the ROTEM Delta instrument either in the blood bank or in the OR.

# **CONSENT**

Consent will not be obtained at the level of the individual patient prior to transfusion because both products are FDA approved and considered standard of care. This is a quality improvement study to understand whether improved logistics (i.e. more ready and immediate access to cryo) can avoid the use of other unnecessary blood products and decrease costs associated with those products. In addition, there is no accurate method to predict the need for fibrinogen replacement in bleeding patients during surgery so consent could not be obtained prior to surgery. The decision to transfuse cryo during surgery occurs urgently during hemorrhage while patients are under anesthesia.

All CV and LT patients will be retrospectively provided with a patient information sheet about
the study after the transfusion in the OR.
All decisions about when to transfuse will be made by clinical providers
according to their clinical judgement and unrelated to the study.

### STATISTICAL ANALYSIS

#### RATIONALE FOR A CLUSTER RANDOMIZED TRIAL

Individual patient efficacy clinical trials are useful to establish the clinical efficacy of an intervention amongst a carefully selected population under optimal conditions following detailed protocols. However, such trials do not address questions about how an intervention or logistical change affects clinical practice in the real world.

The surgical care of patients in our hospital is undertaken using standardized procedures that optimize outcomes, such as standard preoperative assessment and pre-and postoperative care pathways. Because our cardiac surgery and liver transplant services deliver care through standard institutional policies, it is appropriate to address whether either of the two FDAapproved blood products for fibrinogen replacement in acquired hypofibrinogenemia used during surgery to treat bleeding would reduce the total amount of blood products transfused. Testing the effects of the two products mandates a pragmatic trial done with randomization of product used by month rather than by patient. It is extremely difficult to predict which patients will receive fibrinogen replacement during surgery and thus impossible to predict which patients to consent ahead of time. At the time the decision is made to transfuse cryoprecipitate, a patient is already bleeding and under anesthesia, and thus there is no opportunity to consent in real time. Thus, this study will use a cluster randomization treatment assignment design with a calendar month time period as the cluster; specifically addressing whether the use of cryoprecipitate or PR cryoprecipitate reduces overall blood transfusions without any contamination of study groups by the inability to fulfill the appropriate cryo use if individual randomization had been used.

The main challenge of a cluster-randomized trial is the need for inflated sample size (relative to a non-clustered design) that results from clustering. Individuals within a cluster tend to have a smaller degree of variation compared to the variation between clusters, which is measured statistically by the intra-cluster correlation coefficient (ICC) (Arnup SJ et al). If the ICC is greater than 1, then this cluster effect will incorrectly reduce the standard error of the model estimates

if it is not properly accounted for in the analysis. This study will use randomization between intervention arms each month with a design known as the cluster randomized trial. This allows for the ability to assure that all research subjects in a given month will receive a particular cryo product and ensure the reduction in contamination of the two study arms (one of the primary reasons for designing studies in this fashion). In the planned trial, each month the Weill Cornell blood bank will be randomized to one of the two cryoprecipitates as part of a quality improvement study, the randomized product will be used as standard institutional policy for an entire calendar month. At the end of each month, the blood bank is re-randomized to a new standard policy that is used for the subsequent calendar month. This design is methodologically rigorous and tests the effect of a change in standard policy as it would actually be used in the clinical setting.

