### INTRODUCTION

Cryoprecipitated AHF product (cryo), a pooled product from 5-10 blood donors, is the primary source of fibrinogen replacement for bleeding patients in the United States. When stored frozen, it has a shelf life of one year; however, it must be thawed prior to use. Thawing, labeling and dispensing cryo can take 28-97 minutes and then it must be transfused within 6 hours due to a theoretical risk of bacterial contamination.

The competing need to have cryo rapidly available for urgent transfusions and the need to avoid wasting product has led to the development of pathogen reduced (PR) cryo, which recently received FDA approval. This product is also called Intercept Fibrinogen Complex (IFC) and can be kept thawed at room temperature for up to 5 days after thawing.

PR cryoprecipitate is derived from a traditional cryoprecipitate product that is treated with amotosalen.

The inactivation of pathogens

[figure not shown]
allows thawed PR cryo to have a shelf-life of 5 days without the risk of microbial contamination. Furthermore, multiple studies have shown that fibrinogen is stable when thawed at room temperature for up to 35 days. The longer shelf-life should reduce product wastage which

would offset the increased cost of PR cryo over traditional cryo. In vitro studies have shown no differences in efficacy between traditional and PR cryo. No safety differences are expected between the two products, as evidenced by the FDA approving PR cryo without any clinical studies.

The same pathogen reduction process used for PR cryo/IFC that was developed by Cerus Corporation has been in use in the United States since 2014 for platelet and plasma products. Cryoprecipitate is a derivative of plasma, and the pathogen reduction process was already FDA approved. Therefore, the FDA approved this blood product and its pathogen inactivation process, without any clinical trials or observational studies.

PR cryo/IFC, the product we are studying, is a biological blood component and the process used to treat PR cryo, known as INTERCEPT® Blood System for Cryoprecipitation (package insert included in IRB application) is the same process used for PR platelets and PR plasma. The pathogen reduction process occurs at the blood supplier and then the product is received by

[figure not shown]

[figure not shown]

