Since PR cryo can be kept at room temperature for 5 days, similar to thawed plasma, the blood bank can opt to have a PR cryo supply thawed and immediately available for use. This can prevent delays in treatment in bleeding patients.

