### **STUDY DESIGN**

Given that PR cryo can be more readily available for urgent perioperative need, the transfusion medicine service and anesthesiologists at NYP/WC would like to transition to this product. PR cryo is a more expensive product, so it is necessary to evaluate whether its availability will reduce the need for other blood products or reduce traditional cryo wastage, prior to fully converting to this product. A single center prospective, pilot cluster randomized study with an adaptive design will be used to compare the availability and cost effectiveness of cryo and PR cryo when it is ordered for standard clinical indications. In this design, the intervention and randomization are not made at the level of the individual patient, but rather on clusters of patients by month. The clusters will include all patients at NYP/WC for whom pooled cryo is ordered during a single month, not just liver transplant and cardiovascular surgery patients.

Since both products are considered clinically equivalent, the blood bank will alternate use of PR cryo and regular cryo each month for all patients with a cryo order over a one year period during the transition to the use of this new product. All patients will receive either traditional cryo or PR cryo in a given month; however, only a subset (CV and LT patients) will be studied.

Data from the EMR and lab systems will be collected from the NYP data warehouse during the one-year QA study and included in the data analysis. The following demographic variables will be collected: age, ethnicity, race, gender, underlying diseases, surgery type, medications given within 5 days of surgery.

The primary outcome will be the total number of blood components (RBCs, platelets, plasma) used over the admission within the first 30 days after surgery.

REDCap will be used for data collection/storage. Our data scientist, who is an Epic Clinical Data Navigator (CDN), will use SQL queries through the NYP Jupiter data warehouse for automated data extractions of clinical and laboratory data. A TRAC request will be submitted once the IRB is approved. Any variables not available through Jupiter will be extracted manually from the electronic medical record by the research coordinator and entered manually in REDCap. We will use the Safe Harbor method for de-identification of data. We will remove all 18 PHI elements referenced by HHS that could identify a patient.

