The secondary outcomes, which are all routinely available in the EMR per standard of care, will include:

1. Number of cryo or fibrinogen concentrate products used perioperatively (defined as anesthesia start time to 3 days post-procedure)

- 2. Number of RBC, plasma, and platelet products used perioperatively (defined as anesthesia start time to 3 days post-procedure)
- 3. Time from OR start time to start of cryo transfusion
- 4. Time from cryo order to start of transfusion
- 5. Number of cryo units wasted by blood bank per month during study periods.
- 6. Laboratory measures, as available in the medical record, related to the indications for cryo: pre and post transfusion FIBTEM amplitude at 10 mins and maximum clot firmness & fibrinogen level within 10 minutes to one hour after the end of the first cryo transfusion.
- 7. Highest and lowest fibrinogen level or ROTEM FIBTEM within 24 hours after surgery.
- 8. Volume in drains (e.g. chest tube for CV surgery) at 24 hours or until removed, whichever is sooner.
- Time from end of bypass pump until end of surgery (reflects time to hemostasis) for CV surgery
- 10. Length of stay (OR, ICU and hospital)
- 11. Need for ventilator
- 12. Time on ventilator
- 13. Overall cost of cryo vs PR cryo, when factoring wastage, during each 1-month period
- 14. Adverse events: fevers, infections, transfusion reactions within 5 days of surgery start time, need for surgical re-exploration, multiorgan system failure
- 15. Fibrinogen level most proximal to end of procedure

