### Exclusion criteria:

- 1) Patients who do not receive any cryo product in the OR.
- 2) Patients who are not cardiovascular surgery or liver transplant patients
- 3) Cardiac transplantation surgery
- 4) Patients who receive a product in error within either the cryo time period or the PR cryo time period. For example, PR cryo during a cryo month or cryo during a PR cryo time month.
- 5) Patients who receive less than 1 pool (5 units) of cryo
- 6) Pediatric patients (less than 18 years of age).
- 7) Patients who received both PR cryo and traditional cryo
- 8) Pregnant women

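### In-date thawed PR cryo left at a switch to a cryo month can distort the wastage and cost comparisons, in a direction the plan does not settle

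*Combined protocol and SAP*

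**What the plan says.** The Summary makes thawing in advance part of what is compared: the study concerns PR cryo that is thawed and ready before it is ordered. The Introduction says that "the blood bank can opt to have a PR cryo supply thawed and immediately available for use".

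The two products differ sharply once thawed. PR cryo "can be kept thawed at room temperature for up to 5 days after thawing". For traditional cryo, "it must be transfused within 6 hours due to a theoretical risk of bacterial contamination".

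One product is used across the hospital each month. Study Design states: "All patients will receive either traditional cryo or PR cryo in a given month". The cluster-randomization rationale under Statistical Analysis says "the randomized product will be used as standard institutional policy for an entire calendar month". Exclusion criterion 4 treats the other product as an error, giving as its example "PR cryo during a cryo month or cryo during a PR cryo time month".

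The switching scheme is described in two ways. Study Design says "the blood bank will alternate use of PR cryo and regular cryo each month"; the rationale section has the blood bank randomized afresh at each month end.

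Secondary outcome 5 in Study Design is "Number of cryo units wasted by blood bank per month during study periods"; the matching item under Evaluation of Product Superiority counts wasted units per day. Secondary outcome 13 is cost per one-month period, including wastage. Study Design gives the purpose: before full conversion to the dearer product, to learn whether it reduces use of other blood products or wastage of traditional cryo.

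No section says what happens to thawed PR cryo left at a month boundary, which period or product its loss is charged to, or how much thawed stock is held. No transition period is described.

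**The concern.** A thawed PR pool with days of life left on the last day of a PR month could be issued the next day if PR cryo were permanent policy. In the trial, if the next month is a cryo month, it cannot be issued within the protocol. Traditional cryo stays frozen for up to a year and lasts only hours after thawing, so a switch in the other direction strands almost nothing.

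The loss is thus a product of the switching schedule, yet the wastage and cost outcomes as written would count it along with ordinary expiry. Those outcomes inform whether to convert, and conversion would remove the loss. Cost is compared by month, so a one-year study yields only about six values per product, and a repeated addition to one side can move the ranks in a Wilcoxon test. A total discard count cannot later be split into changeover loss and ordinary expiry, so the distinction must be captured as discards occur.

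**Working it through.** **1. The plan's own calculation.** The only design calculation is for the primary endpoint (Sample Size Analysis: ratio of means 0.8, coefficient of variation 1.1, 80% power, two-sided 5%).

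- SD on the log scale = sqrt(ln(1 + 1.1²)) = 0.8905; ln 0.8 = −0.2231.
- n per group = 2 × [0.8905 × (1.960 + 0.842) / 0.2231]² = 250.
- Design effect = 1 + 99 × 0.0001 = 1.0099, giving 252.5, or 253.

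The stated 251 is reproduced to within 1%. Wastage does not enter it. No calculation is given for wastage or cost.

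**2. How often a PR month is followed by a cryo month** (12 months, 11 boundaries).

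- Alternation: 6 PR months, so 6 switches if PR cryo comes first. If traditional cryo comes first there are 5, or 6 if use reverts after month 12.
- Independent monthly randomization: 11 × 1/2 × 1/2 = 2.75 expected.
- Random order with six months each: 11 × (6/12) × (6/11) = 3 expected.

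Essentially every PR month end is affected under alternation, and about half under re-randomization.

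**3. Extra discard per switch.** Stock level and hospital-wide demand are not in the documents, so both are assumed. The lowest demand is tied to the Interim Analysis section: 302 patients in about a year is 302/12 ≈ 25 a month, and at one pool each 25/30 = 0.83 pools a day. Higher values allow for more pools per patient and for patients outside the study.

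The simulated model has a 30-day month, stock topped up daily to S pools, a 5-day life, oldest pool issued first and Poisson demand. It compares pools wasted per month under continuous PR use with pools wasted when remaining stock is discarded at month end and the next PR month starts fresh.

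| Demand per day | S | Continuous use | With month-end discard | Net extra |
|---|---|---|---|---|
| 0.83 | 2 | 1.3 | 2.4 | 1.1 |
| 0.83 | 4 | 6.5 | 9.0 | 2.5 |
| 0.83 | 8 | 25.1 | 30.3 | 5.2 |
| 1.67 | 2 | 0.05 | 0.73 | 0.7 |
| 1.67 | 4 | 0.75 | 3.0 | 2.3 |
| 1.67 | 8 | 8.9 | 14.4 | 5.5 |
| 3.3 | 2 | 0.0 | 0.2 | 0.2 |
| 3.3 | 4 | 0.0 | 1.1 | 1.1 |
| 3.3 | 8 | 0.2 | 4.9 | 4.7 |

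The net extra runs from 0.2% of monthly demand (0.2 of 99 pools) to 21% (5.2 of 24.9 pools). It cannot exceed S pools per switch, and it is zero if no stock remains.

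**4. What leaving out all changeover discards would do.** With 8 pools held and 0.83 a day, about 6.1 pools remain at month end. Dropping them leaves 30.3 − 6.1 = 24.2 pools wasted, against 25.1 under continuous use: about 0.9 pools too few. This is the largest such gap in the grid; with 4 pools held and 1.67 a day it is about 0.1.

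**The case against.** **Discard is inferred.** A reader might infer that the design forces thawed PR cryo to be thrown away. No section says so. Holding thawed stock is worded as an option, exclusion criterion 4 governs who is analysed, and the blood bank controls thawing and could let stock run down. That stands. Running down has a price, however: in the model with 4 pools held and 1.67 a day, no top-up in the last five days leaves nothing over, but demand not met from thawed stock rises from about 1.1 to 5.4 pools a month. That reduces the ready availability under test. If the next month's product is drawn only at month end, the blood bank may also not know in time.

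**The direction is open.** A reader might infer that the comparison is biased against PR cryo. That holds if the loss is charged to the PR product or month. Stock thawed late in a PR month can reach its expiry days into the cryo month; logged by date, it would count against traditional cryo. Neither outcome list gives a rule.

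**No minimum can be derived.** It is tempting to divide 30 days by 5, get six stock cycles, and claim at least 1/6 = 17% extra. One stock per switch is a ceiling. If every cycle expired unused, the sixth would expire on day 30 anyway and the switch would add nothing. Replenishment as stock is used also breaks the six-cycle count.

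**The daily definition softens the effect.** If wastage is analysed per day, a changeover-day discard touches about 1 day in 30, and a rank test limits its influence. This is fair for outcome 5; the monthly cost outcome stays exposed.

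**Conclusion.** The concern holds as a minor point about two secondary outcomes. In-date thawed PR cryo left at a PR-to-cryo switch has no permitted use and would probably be discarded. Traditional cryo has almost no matching loss, and full conversion would not cause one. Wastage and cost counted as written could therefore mix an effect of the schedule with an effect of the product.

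Across the assumed stock and demand values the net extra is about 0.2 to 5.5 pools per switch. With 4 pools held and 1.67 a day, monthly waste rises about fourfold, from 0.75 to 3.0 pools. These figures show that the effect may be negligible or material; they are not estimates for this blood bank. Neither a certain discard nor a fixed direction of bias is supported by the documents. The primary endpoint and its sample size are untouched.

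**What to change.** - Record a reason and thaw date for every discarded unit, with changeover as its own reason.
- State in the analysis plan that changeover discards are charged to the product discarded, whatever the date logged.
- Report outcomes 5 and 13 with and without changeover discards. Note that the version without them slightly favours PR cryo, because some of those units would have expired anyway.
- Reconcile alternation in Study Design with monthly re-randomization in the rationale section, and wastage per month in the outcome list with wastage per day in the analysis list.

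The cost is a small addition to the blood bank log and a few sentences in the plan. Classifying a discard needs a small judgement by staff who know the assigned product; the thaw date makes it checkable, and reporting both versions limits what depends on it.

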#### **SAMPLE SIZE ANALYSIS**

The primary endpoint of the study is total number of blood components other than cryo (RBCs, platelets, plasma) used over the hospital admission within the first 30 days after surgery. The goal of the trial is to demonstrate a 20% reduction in this total blood product use for PR cryo compared to the total observed with conventional cryo. In order to determine this effect size and the patient variability associated with this outcome, data were collected from 150 cardiovascular surgery and liver transplant cases at the study center during 6 months in 2021. Because the number of units used was clearly right-skewed and, therefore, possibly lognormally distributed, the sample size determination was based on the hypothesized ratio of means (effect size) of 0.8. In addition, the coefficient of variation is the key determinant of variability with log-normal data, and this was seen with the recent data to be a value of 1.1. The other issue to consider in this calculation is the cluster randomization. However, the cluster in this study is the month when the surgery is performed. The assumption is made that the intracluster correlation of the primary outcome within a given month should be very small, say 0.0001. As a result, this would have very little effect on the sample size (the Kish design effect is about 1.01 assuming approximately 100 subjects per month). Then with 80% power and 5% significance (two-sided), the number of subjects per group would be 251.

However, there is a possibility that the effect size has been overestimated. Thus, a sample size re-estimation will be conducted after 60% of the subjects have been included in the trial. The method of Gould (Gould AL. Interim analyses for monitoring clinical trials that do not materially affect the type I error rate. Stat Med 1992; 11:55-66.) will be used to re-evaluate the sample size.

# **EQUIVALENCY BETWEEN COHORTS**

In order to control for possible patient population variations between the patients transfused with cryo and PR cryo, clinical scoring systems will be utilized to ensure the two groups are similar: MELD score for liver transplant patients and EUROSCORE for cardiovascular surgery patients.

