#### **EVALUATION OF PRODUCT SUPERIORITY**

The primary outcome of total number of blood components (RBCs, platelets, plasma) used over the admission within the first 30 days after surgery will be evaluated using a two-sample t-test on the log-transformed values or the Wilcoxon rank-sum test if the log-transform does not result in an acceptable comparability to a normal distribution. This will be based on an intent-to-treat paradigm (all subjects randomized will be evaluated and in the group they were randomized to). However, it is assumed that all of the subjects will be appropriately evaluated for this endpoint.

There are a number of secondary endpoints, and the specific statistical method is indicated below:

- 1. Number of cryo or fibrinogen concentrate products used perioperatively (defined as anesthesia start to 24 hours post-procedure): Wilcoxon rank-sum test
- 2. Number of RBC, plasma, and platelet products used perioperatively (defined as anesthesia start to 24 hours post-procedure): Wilcoxon rank-sum test
- 3. Time from cryo order to ready in the blood bank: Wilcoxon rank-sum test
- 4. Time from cryo order to start of infusion: Wilcoxon rank-sum test
- 5. Number of cryo units wasted by blood bank per day during study periods: Wilcoxon rank-sum test
- 6. Laboratory measures for cryo and PR cryo (pre and post transfusion FIBTEM amplitude at 10 mins and maximum clot firmness, fibrinogen): Wilcoxon rank-sum test
- 7. Volume in mediastinal drains (e.g. chest tube for CV surgery) at 24 hours (or until removed): Wilcoxon rank-sum test
- 8. Length of stay (OR, ICU and hospital) & time on ventilator: log-rank test, particularly if there is any censoring
- 9. Overall cost of cryo vs PR cryo, when factoring wastage, during each 1-month period: Wilcoxon rank-sum test
- 10. Fibrinogen level most proximal to end of procedure, with adjustment for fibrinogen dose administered (if known): without adjustment the Wilcoxon rank-sum test can be used; with adjustment a properly selected linear model (depending on the link function required)

[figure not shown]
In order to control statistical significance for this number of endpoints, the Holm procedure will be used.

[figure not shown]
Many of the endpoints noted above can be evaluated after adjustment with selected covariates using a properly selected linear model (depending on the link function required).

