### **INTERIM ANALYSIS**

A separate interim analysis for futility will be conducted on the primary endpoint when 60% of the subjects have completed the trial. Sixty percent of 502 (251 per group) is 302. We expect to accrue 302 patients in approximately 1 year. During the interim analysis we will decide if the study will continue or stop. This will involve the calculation of conditional power and a potential stopping rule of a value for this calculation of <10%.

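### The primary test is pooled and unadjusted, and the MELD/EuroSCORE comparison does not replace adjustment: prespecify a model with surgery type and both scores

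*Combined protocol and SAP*

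**What the plan says.** The section EQUIVALENCY BETWEEN COHORTS sets out to control for population differences between patients given the two products. Its only measure is that "clinical scoring systems will be utilized to ensure the two groups are similar": MELD in liver transplant (LT), EuroSCORE in cardiovascular (CV) surgery. It gives no test, no threshold, no consequence if the groups differ, and no link to a model.

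EVALUATION OF PRODUCT SUPERIORITY states that the primary outcome "will be evaluated using a two-sample t-test on the log-transformed values", or by a Wilcoxon rank-sum test if the logs are not acceptably normal. Neither test has a term for surgery type or for either score. The same section closes with "Many of the endpoints noted above can be evaluated after adjustment with selected covariates". It does not say which covariates, whether the primary endpoint is among these endpoints, or which result would govern.

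The variables listed in STUDY DESIGN include "underlying diseases, surgery type, medications given within 5 days of surgery". MELD and EuroSCORE are not in that list. Allocation is by month: "each month the Weill Cornell blood bank will be randomized to one of the two cryoprecipitates". No stratification by surgery type is described.

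**The concern.** A comparison of scores between arms describes the groups; it does not control for anything, because the estimated product effect is the same whatever the comparison shows. This comparison also has a blind spot. MELD can balance among transplant patients and EuroSCORE among CV patients while one arm holds more transplant patients than the other. The collected surgery type could reveal that, but the plan gives it no role in the primary analysis.

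If the two services use different numbers of components, two things are lost. Between-service variation stays in the error term, so the interval is wider than it need be. And a chance difference in transplant share passes uncorrected into the estimate. With few randomized months such differences are a practical possibility. Leaving the covariates open until the data are seen also means that an adjusted result, if produced, would not have been protected by prespecification.

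**Working it through.** **Inputs from the documents.** Ratio of means 0.8, coefficient of variation 1.1, 80% power, 5% two-sided, 251 per group (SAMPLE SIZE ANALYSIS). "We expect to accrue 302 patients in approximately 1 year" and a total of 502 (INTERIM ANALYSIS). "data were collected from 150 cardiovascular surgery and liver transplant cases at the study center during 6 months in 2021" (SAMPLE SIZE ANALYSIS).

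**Assumed, because the documents give no value.** Transplant share p of 15% to 35%; ratio r of typical component use between the services of 1.5 to 3.

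**1. The plan's figure.** Log variance = ln(1 + 1.1²) = 0.793, SD 0.8905. Effect = −ln 0.8 = 0.2231. n = 2 × (1.960 + 0.842)² × 0.793 / 0.2231² = 250 per group; the exact t calculation gives 251. So 251 is the size of an unadjusted, pooled comparison. Its standard error is √(0.793 × 2/251) = 0.0795.

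**2. What surgery type could explain.** R² = p(1 − p)(ln r)² / 0.793. The interval narrows by 1 − √(1 − R²). Power, month ignored, is Φ(0.2231 / [0.0795 √(1 − R²)] − 1.96). The last column uses the noncentral t on 18 degrees of freedom (step 3).

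| p | r | R² | Interval narrower by | Power, month ignored | Power, 18 df |
|---|---|---|---|---|---|
| any | 1 | 0 | 0 | 80.2% | 75.6% |
| 0.15 | 1.5 | 0.026 | 1.3% | 81.2% | 76.8% |
| 0.25 | 2 | 0.114 | 5.9% | 84.7% | 80.5% |
| 0.35 | 3 | 0.346 | 19.1% | 93.5% | 90.7% |

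**3. Number of months.** 302/12 = 25.2 patients per month, which agrees with 150/6 = 25 in the 2021 data. 502/25.2 is about 20 months, so a month-level error term has about 20 − 2 = 18 degrees of freedom. Without covariates 251 per group then gives about 76% power. Reaching 80% needs R² of about 0.102; at p = 0.25 that means r of about 1.93.

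**4. Chance imbalance.** A difference D in transplant share shifts the unadjusted log ratio by D × ln r. With p = 0.25 and a share that is stable over months, the chance SD of D is √(0.25 × 0.75 × 2/251) = 0.039. At r = 2 a one-SD difference shifts the estimate by 0.039 × 0.693 = 0.027, or 12% of the planned effect. A 10-point difference would shift it by 0.069, or 31%, but is about 2.6 SDs out (0.10/0.039).

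**5. Type I error of the patient-level t-test.** If the underlying share varies by month with SD s, the intracluster correlation from this source is s²(ln r)²/0.793. With 25 patients per month the design effect is 1 + 24 × ICC, and the rejection rate under the null is 2[1 − Φ(1.96/√DE)]. At mean share 25%:

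| r | s = 0.05 | s = 0.10 |
|---|---|---|
| 1.5 | 5.1% | 5.6% |
| 2 | 5.4% | 6.7% |
| 3 | 6.1% | 9.3% |

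Simulation of 20 months with 25 patients each agrees closely (6.2% at r = 3, s = 0.05). In the same simulation at s = 0.10, comparing unadjusted month means on 18 df rejects 5.0% of the time. Handling month therefore removes the inflation without any covariate.

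**The case against.** The strongest objection is that an unadjusted comparison of randomized groups is valid. That stands, provided month is handled. A reader might infer from step 5 that omitting surgery type inflates the type I error. The documents do not support this: the inflation comes from treating patients as independent when months were randomized, and it belongs to the separate question of clustering. Adjusting for surgery type removes only the part that arises from a varying transplant share; any other month effect would remain. The s = 0.10 column is also a strong assumption: it implies a case-mix intracluster correlation of 0.01/(0.25 × 0.75) = 0.053, and no section supports it. On the other side, the plan's own outcome correlation is itself only an assumption ("The assumption is made that the intracluster correlation of the primary outcome within a given month should be very small, say 0.0001"), and at r = 2 it leaves room for a monthly share SD of only √(0.0001 × 0.793)/0.693 = 0.013.

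Second, the gain may be small. At the low end the interval narrows by 1.3%, and nothing in the documents shows that component use differs by service. STUDY PATIENT POPULATION notes different mechanisms but a shared pattern of coagulopathy, and calls the two groups fairly homogeneous. This stands as a limit on size, not as a reason to leave the covariates unnamed.

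Third, the plan permits adjustment and collects surgery type, so it cannot be said that adjustment is absent or that the transplant share could never be tabulated. What is missing is a stated choice of covariates and a statement of which analysis is primary.

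Fourth, the contribution of MELD and EuroSCORE has not been sized. That is so; they are proposed because the plan itself singles them out as the measures of patient risk.

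**Conclusion.** The point holds as one of prespecification. The score comparison affects no estimate and cannot detect a different transplant share, and the primary test uses none of the baseline information that the plan considers important. The cost is precision and protection against chance case-mix imbalance: an interval 1% to 19% wider than necessary in the assumed settings, and nothing if component use is the same in both services. If month is handled, the covariates may decide whether 251 per group still delivers 80% power, since about 76% is available without them.

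It should not be read as a finding that the unadjusted estimate is systematically biased, nor that adjustment would repair everything. In particular, Exclusion criteria limit the analysis to patients who receive cryo in the operating room, and baseline adjustment does not remove any selection on unmeasured bleeding severity. This is a change that should be made; confidence is medium because share, use ratio and R² are all assumed.

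**What to change.** In EQUIVALENCY BETWEEN COHORTS and EVALUATION OF PRODUCT SUPERIORITY:

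- Prespecify as primary the product effect from a linear model of log component count with product and surgery type (LT or CV), adding MELD within LT and EuroSCORE within CV as prognostic covariates, each the last value before surgery and centred within type.
- Add both scores to the variable list in STUDY DESIGN. Impute a missing score with the within-type mean, without regard to arm, so that no randomized patient is dropped.
- Replace the Wilcoxon fallback with a version stratified by surgery type (van Elteren test).
- Use whatever month-level error term is adopted for clustering, in the model and in the fallback.
- Keep the unadjusted test as a sensitivity analysis. Report transplant share and both scores by arm.
- State that adjustment does not remove selection on unmeasured bleeding severity.

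Before finalizing, the sponsor can estimate transplant share, use by service and R² in its own 150 cases, including whether R² reaches the roughly 10% needed for 80% power on about 18 degrees of freedom.

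The cost is revised wording, extraction of two scores, a little more analysis work, and a few degrees of freedom if the covariates prove not to be prognostic. The covariates themselves need no extra patients; the power cost comes from handling month.
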